3.1.1 Child Bearing Potential

- Female subject is either post-menopausal, surgically sterilized, or willing to use an acceptable method of birth control (i.e., a hormonal contraceptive, intra-uterine device, diaphragm with spermicide, condom with spermicide, or abstinence) for the duration of the study. Women of childbearing potential (WOCBP) must have a negative serum or urine pregnancy test (minimum sensitivity 25 IU/L or equivalent units of HCG) within 24 hours prior to the start of nivolumab.
- Men who are sexually active with WOCBP must use any contraceptive method with a failure rate of less than 1% per year. Men receiving nivolumab and who are sexually active with WOCBP will be instructed to adhere to contraception for a period of 31 weeks after the last dose of investigational product. Women who are not of childbearing potential (i.e., who are postmenopausal or surgically sterile) as well as azoospermic men do not require contraception.

3.1.2 Informed Consent

All participants will undergo standard written informed consent procedures as dictated by the City of Hope Human Research Protections Office prior to performing any screening procedures that are not part of standard-of-care. Informed consent will be obtained by the principal investigator, collaborating investigators, or other IRB designated personnel who will meet the training requirements established by the IRB. With the support of research personnel, he/she will explain the nature, duration, purpose of the study, potential risks, alternatives and potential benefits, and all other information contained in the informed consent document. In addition, they will review the experimental subject's bill of rights and the HIPAA research authorization form. Prospective research participants will be informed that they may withdraw from the study at any time and for any reason without prejudice. Prospective research participants will be afforded sufficient time to consider whether or not to participate in the research.

3.1.3 Prior Therapy

Patient must be either refractory to or relapsed after 1 line of therapy.

Prior radiation therapy is allowed.

3.2 **Exclusion Criteria**

- Prior exposure to PD-1 or PD-L1 inhibitors is not allowed
- Must not have had second line chemotherapy for Hodgkin lymphoma.
- Active autoimmune diseases requiring systemic treatments.
- Vaccinated with live, attenuated vaccines within 4 weeks of first dose of study drug.
- Any life-threatening illness, medical condition, or organ system dysfunction that, in the investigator's opinion, could compromise the subject's safety or put the study outcomes at undue risk.
- Unwilling or unable to participate in all required study evaluations and procedures.
- Unable to understand the purpose and risks of the study and to provide a signed and dated informed consent form (ICF) and authorization to use protected health information (in accordance with national and local subject privacy regulations).
- Patients should not have any uncontrolled illness including ongoing or active infection.
- Patients may not be receiving any other investigational agents, or concurrent biological therapy, chemotherapy, or radiation therapy.
- Patients must not have received prior chemotherapy or radiation for ≤ 3 weeks before study enrollment, or those who have not recovered from the adverse events due to agents administered more than 3 weeks earlier are excluded.
- Myocardial infarction within 6 months prior to enrollment or New York Heart Association (NYHA) Class III or IV heart failure, uncontrolled angina, severe uncontrolled ventricular arrhythmias, or electrocardiographic evidence of acute ischemia or active conduction system abnormalities. Prior to study entry, any ECG abnormality at screening has to be documented by the Investigator as not medically relevant.
- Significant screening electrocardiogram (ECG) abnormalities including, but not limited to, left bundle branch block, 2nd degree atrioventricular (AV) block type II, 3rd degree block, or corrected QT interval (QTc) ≥ 470 msec. Subjects with a cardiac pacemaker who have a QTc interval of ≥ 470

msec may be eligible if these findings are considered not clinically significant as documented via a cardiology evaluation.

- DLCO <60%. The clinical studies in support of accelerated approval for nivolumab in cHL after failure of ASCT required DLCO > 60%. Certain HL induction regimens have the potential for pulmonary toxicity, and nivolumab carries the potential of pneumonitis or other pulmonary toxicities.
- Diagnosed or treated for another malignancy within 3 years of enrollment, with the exception of complete resection of basal cell carcinoma or squamous cell carcinoma of the skin, an in situ malignancy, or low-risk prostate cancer after curative therapy.
- Patients with active CNS disease or history of brain metastases are excluded from study.
- Patients should be excluded if they have a condition requiring systemic treatment with either corticosteroids (> 10 mg daily prednisone equivalents) or other immunosuppressive medications within 14 days of study drug administration. Inhaled or topical steroids and adrenal replacement doses > 10 mg daily prednisone equivalents are permitted in the absence of active autoimmune disease.
- Pregnant women are excluded from this study because of the potential for teratogenic or abortifacient effects. Because there is an unknown but potential risk for adverse events in nursing infants secondary to treatment of the mother, breastfeeding should be discontinued.
- Recent infection requiring systemic treatment that was completed \leq 14 days before the first dose of study drug.
- Known active hepatitis B virus (HBV) or hepatitis C virus (HCV) infection. Patients with past HBV infection (defined as negative HBsAg and positive hepatitis B core antibody [HBcAb]) are eligible if HBV DNA is undetectable. Patients who are positive for HCV antibody are eligible if PCR is negative for HCV RNA. Testing to be done only in patients suspected of having infections or exposures.
- Known active human immunodeficiency virus (HIV) infection. Subjects who have an undetectable or unquantifiable HIV viral load with CD4 > 300 and are on HAART medication are allowed. Testing to be done only in patients suspected of having infections or exposures.
- History of allergy or adverse drug reaction to study components.

3.3 Inclusion Criteria for Cohort B

In addition to the inclusion/exclusion criteria as outlined above, to be eligible for treatment in the new cohort patients must have high-risk disease, defined as having any one of the following:

- B symptoms at relapse
- Extranodal disease at relapse
- Primary refractory disease
- Relapsed < 1 year after completion of frontline therapy
- have received brentuximab vedotin as initial therapy

3.4 Inclusion of Women and Minorities

The study is open to anyone regardless of gender or ethnicity. Efforts will be made to extend the accrual to a representative population. If differences in outcome that correlate to gender, racial, or ethnic identity are

noted, accrual may be expanded or additional studies may be performed to investigate those differences more fully.

4 Participant Enrollment

4.1 Pre-Enrollment Informed Consent and Screening Procedures

The investigational nature and objectives of the trial, the procedures and treatments involved, their attendant risks and discomforts, and potential alternative therapies will be carefully explained to the subject, and a signed informed consent will be obtained. Documentation of informed consent for screening will be maintained in the subject's research chart and medical record.

Diagnostic or laboratory studies performed exclusively to determine eligibility will be done only after obtaining written informed consent. Studies or procedures that were performed for clinical indications (not exclusively to determine study eligibility) may be used for baseline values, even if the studies were done before informed consent was obtained. Screening procedures are listed in **Section 9.0 Study Activity Calendar**.

4.2.2 Slot verification and reservation

As the study accrues, study team personnel (including physicians, protocol nurses and/or CRCs) may wish to contact the DCC to verify slot availability and to reserve an open slot or be placed in queue for slot opening. Slots may only be held for a limited time, which will be determined by the Protocol Monitoring Team. The Data Coordinating Center should be notified of cancellations of prospective participants holding slots as soon as possible.

4.2.3 Registration procedure

To register a participant, the subsequent procedure is to be followed:

The participating site's data manager/coordinator/research nurse should contact the DCC via telephone or email to provide notification regarding the pending registration and communicate the desired timeline of the registration, especially if it must be completed promptly to meet the registration window.

The data manager/coordinator/research nurse should then e-mail copies to [contact] of the following documents to the DCC:

- Registration Cover Sheet (non-COH sites only) (see Appendix A)
- Completed Eligibility Criteria List (printed from Section 3.0 of the protocol)
- Source documentation to support eligibility criteria*
- Signed informed consent document
- Signed HIPAA authorization form (if separate from the informed consent document)
- Signed subject's Bill of Rights (COH only)

*For COH participants, provide copies of source documentation only if not readily available as a finalized record in the COH EMR.

After having received all documentation, the DCC will complete the review of the documents to verify eligibility, working with COH staff or the participating site staff as needed to resolve any missing required source elements. A subject failing to meet all protocol eligibility requirements will not be registered.

Once eligibility has been confirmed, the DCC staff will register the participant by assigning a subject accession number, register the subject on study centrally into MIDAS for outside institutions (the COH CRC will directly access into MIDAS), and enter the subject into the eCRF system, Medidata RAVE.

Once registration has been completed, DCC staff will send a Confirmation of Registration Form, including the participant study number and dose level assigned, to the following:

- the site study team: site PI, treating physician, protocol nurse, and CRC
- the COH Protocol Monitoring Team: [name], [name] and the COH CRN and CRC.

4.3 Dose Level Assignment

The Data Coordinating Center will be responsible for centrally registering all subjects for this trial and therefore will provide the participating sites the specific information pertaining to the dose level for each patient.

5 Treatment Program

5.1 Treatment Overview

Treatment will be given on an outpatient basis unless patients are already hospitalized for symptoms of Hodgkin lymphoma.

5.1.1 Nivolumab Dose and Administration

Nivolumab will be given at 240 mg IV over approximately 30 minutes (see [Section 5.6.1](#) for allowable infusion interruptions), every 2 weeks in the nivolumab only stage. In the NIVO + ICE stage, nivolumab will be given at 240 mg IV every 3 weeks in combination with ICE.

Subjects may be dosed no fewer than 12 days from the previous dose of drug. There are no premedications recommended for nivolumab on the first cycle.

Subjects should be carefully monitored for infusion reactions during nivolumab administration. If an acute infusion reaction is noted, subjects should be managed according to Protocol Section 5.1.3.

Doses of nivolumab may be interrupted, delayed, or discontinued on the basis of subject tolerance to treatment.

5.1.2 ICE Dose and Administration

The ICE components may be administered as per institutional standard of care. Inpatient or outpatient administration is allowed. Dosing should be based on the patient's baseline (predose, Cycle 1 Day 1) height and weight or per institutional standards at the site. Doses will be adjusted for patients who experience a $\geq 10\%$ change in weight during the study. Rounding is permissible according to institutional standards.

| | Agent | Dose | Route | Schedule (Days within each 21-day cycle) |
|----------------------------|--------------|------------------------|-------|--|
| ICE (Inpatient Schedule)** | Etoposide | 100 mg/m ² | IV | Days 1-3 |
| | Carboplatin | AUC 5 (750 mg max) | IV | Day 2 |
| | Ifosfamide * | 5000 mg/m ² | IV | Day 2 |

* **Outpatient treatment is allowed** and schedule is similar to Inpatient schedule, except for ifosfamide which will be given at a dose of 1670 mg/m² on Days 1-3 (instead of 5000 mg/m² on Day 2). Ifosfamide is always given with Mesna, according to institutional standards.

5.1.3 Nivolumab Required Premedication and Postmedication

Routine premedication should not be administered prior to the first dose of nivolumab. However, patients who experience a Grade 1 or Grade 2 infusion-related reaction may receive subsequent nivolumab infusions with premedication as described in Section 5.6.1 below. Patients who experience a Grade 3 or Grade 4 infusion-related reaction may potentially receive additional treatment with nivolumab at the discretion of the Investigator.

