5.6.1 Management of Nivolumab Infusion Reactions

Since nivolumab contains only human immunoglobulin protein sequences, it is unlikely to be immunogenic and induce infusion or hypersensitivity reactions. However, if such a reaction were to occur, it might manifest with fever, chills, rigors, headache, rash, pruritis, arthralgias, hypo- or hypertension, bronchospasm, or other symptoms of allergic-like reactions.

All Grade 3 or 4 infusion reactions should be reported as an SAE if criteria are met. Infusion reactions should be graded according to NCI CTCAE 4.03 guidelines.

Treatment recommendations are provided below and may be modified based on local treatment standards and guidelines as appropriate:

For Grade 1 symptoms: (Mild reaction; infusion interruption not indicated; intervention not indicated): Remain at bedside and monitor subject until recovery from symptoms. The following prophylactic premedications are recommended for future infusions: diphenhydramine 50 mg (or equivalent) and/or paracetamol 325 to 1000 mg (acetaminophen) at least 30 minutes before additional nivolumab administrations.

For Grade 2 symptoms: (Moderate reaction requires therapy or infusion interruption but responds promptly to symptomatic treatment [e.g., antihistamines, non-steroidal anti-inflammatory drugs, narcotics, corticosteroids, bronchodilators, IV fluids]; prophylactic medications indicated for 24 hours).

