Stop the nivolumab infusion, begin an IV infusion of normal saline, and treat the subject with diphenhydramine 50 mg IV (or equivalent) and/or paracetamol 325 to 1000 mg (acetaminophen); remain at bedside and monitor subject until resolution of symptoms. Corticosteroid or bronchodilator therapy may also be administered as appropriate. If the infusion is interrupted, then restart the infusion at 50% of the original infusion rate when symptoms resolve; if no further complications ensue after 30 minutes, the rate may be increased to 100% of the original infusion rate. Monitor subject closely. If symptoms recur then no further nivolumab will be administered at that visit. Administer diphenhydramine 50 mg IV, and remain at bedside and monitor the subject until resolution of symptoms. The amount of study drug infused must be recorded on the electronic case report form (eCRF). The following prophylactic premedications are recommended for future infusions: diphenhydramine 50 mg (or equivalent) and/or paracetamol 325 to 1000 mg (acetaminophen) should be administered at least 30 minutes before additional nivolumab administrations. If necessary, corticosteroids (recommended dose: up to 25 mg of IV hydrocortisone or equivalent) may be used.

For Grade 3 or Grade 4 symptoms: (Severe reaction, Grade 3: prolonged [i.e., not rapidly responsive to symptomatic medication and/or brief interruption of infusion]; recurrence of symptoms following initial

improvement; hospitalization indicated for other clinical sequelae [e.g., renal impairment, pulmonary infiltrates]). Grade 4: (life threatening; pressor or ventilatory support indicated).

Immediately discontinue infusion of nivolumab. Begin an IV infusion of normal saline, and treat the subject as follows. Recommend bronchodilators, epinephrine 0.2 to 1 mg of a 1:1,000 solution for subcutaneous administration or 0.1 to 0.25 mg of a 1:10,000 solution injected slowly for IV administration, and/or diphenhydramine 50 mg IV with methylprednisolone 100 mg IV (or equivalent), as needed. Subject should be monitored until the investigator is comfortable that the symptoms will not recur. Nivolumab will be permanently discontinued. Investigators should follow their institutional guidelines for the treatment of anaphylaxis. Remain at bedside and monitor subject until recovery from symptoms.

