7.5 Discontinuation Criteria

Treatment should be permanently discontinued for the following:

- Any Grade 2 drug-related uveitis or eye pain or blurred vision that does not respond to topical therapy and does not improve to Grade 1 severity within the re-treatment period OR requires systemic treatment.
- Any Grade 3 non-skin, drug-related adverse event lasting > 7 days, with the following exceptions for drug-related adverse reactions: uveitis, pneumonitis, bronchospasm, hypersensitivity reactions, infusion reactions, and endocrinopathies:
 - Grade 3 drug-related uveitis, pneumonitis, bronchospasm, hypersensitivity reaction, or infusion reaction of any duration requires discontinuation
 - Grade 3 drug-related endocrinopathies adequately controlled with only physiologic hormone replacement do not require discontinuation
- Grade 3 drug-related laboratory abnormalities do not require treatment discontinuation except those noted below
 - Grade 3 drug-related thrombocytopenia > 7 days or associated with bleeding requires discontinuation
 - For patients without liver involvement and without higher AST or ALT levels at baseline, any drug-related liver function test (LFT) abnormality that meets the following criteria requires discontinuation:
 - AST or ALT > 5 x ULN
 - Total bilirubin > 3 x ULN

- For patients with liver involvement (and higher AST or ALT levels at baseline), or those who otherwise have higher AST/ALT levels as allowed in the inclusion criteria, any drug-related liver function test (LFT) abnormality that meets the following criteria requires discontinuation:
 - AST or ALT > 8 x ULN
 - Total bilirubin > 5 x ULN
- Any Grade 4 drug-related adverse event or laboratory abnormality, except for the following events which do not require discontinuation:
 - Isolated Grade 4 amylase or lipase abnormalities that are not associated with symptoms or clinical manifestations of pancreatitis and decrease to < Grade 4 within 1 week of onset.
 - Isolated Grade 4 electrolyte imbalances/abnormalities that are not associated with clinical sequelae and are corrected with supplementation/appropriate management within 72 hours of their onset.
 - Grade 4 lymphopenia or leucopenia.

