- Grade 4 hypophysitis, Grade 3 or 4 adrenal insufficiency, or Grade 4 hyperglycemia. Other Grade 4 drug-related endocrinopathy adverse events, such as ACTH deficiency, hyper- or hypothyroidism, or glucose intolerance other than Grade 4 hyperglycemia, which resolve within 14 days or are adequately controlled with physiologic hormone replacement (corticosteroids, thyroid hormones) or glucose-controlling agents, respectively, may not require discontinuation after discussion with and approval from the Investigator (as allowed by protocol).
- Any dosing interruption lasting > 6 weeks with the following exceptions:
 - Dosing delays or interruptions to allow for prolonged steroid tapers to manage drug-related adverse events are allowed. Prior to re-initiating treatment in a subject with a dosing interruption lasting > 6 weeks, the Investigator must be consulted. Tumor assessments should continue as per protocol even if dosing is interrupted or delayed.
 - Dosing interruptions or delays lasting > 6 weeks that occur for non-drug-related reasons may be allowed if approved by the Investigator. Prior to re-initiating treatment in a subject with a dosing interruption lasting > 6 weeks, the Investigator must be consulted. Tumor assessments should continue as per protocol even if dosing is interrupted.
- Any adverse event, laboratory abnormality, or intercurrent illness which, in the judgment of the Investigator, presents a substantial clinical risk to the subject with continued nivolumab dosing.

8 Agent Information and Risks

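### Section 5.1.3 allows nivolumab again after a Grade 3 or 4 infusion reaction, while Sections 5.6.1 and 7.5 require it to stop for good

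*Combined protocol and SAP*

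**What the plan says.** Four sections of the combined protocol and SAP bear on a severe infusion reaction to nivolumab.

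- **Section 5.1.3** (premedication and postmedication) ends with: "Patients who experience a Grade 3 or Grade 4 infusion-related reaction may potentially receive additional treatment with nivolumab at the discretion of the Investigator".
- **Section 5.6.1** (management of infusion reactions) says in its Grade 3 or 4 paragraph: "Nivolumab will be permanently discontinued". The section's treatment guidance is introduced with a qualifier: "Treatment recommendations are provided below and may be modified based on local treatment standards and guidelines as appropriate".
- **Section 7.5** (discontinuation criteria) opens with "Treatment should be permanently discontinued for the following". Its Grade 3 line reads: "Grade 3 drug-related uveitis, pneumonitis, bronchospasm, hypersensitivity reaction, or infusion reaction of any duration requires discontinuation". Its Grade 4 line reads: "Any Grade 4 drug-related adverse event or laboratory abnormality, except for the following events which do not require discontinuation". The exceptions are isolated amylase or lipase abnormalities, isolated electrolyte abnormalities, low lymphocyte or leucocyte counts, and a group of endocrine events that begins "Grade 4 hypophysitis, Grade 3 or 4 adrenal insufficiency, or Grade 4 hyperglycemia".
- **Section 5.1.1** (dose and administration) tells sites where to look: "If an acute infusion reaction is noted, subjects should be managed according to Protocol Section 5.1.3".

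**The concern.** Whether to give a drug again after a severe or life-threatening reaction to it should have one answer in a protocol. Here 5.1.3 leaves it to the investigator, and 5.6.1 and 7.5 say no. The cross-reference in 5.1.1 makes this worse, because it points to the section with the permissive sentence and no management steps.

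Two things are at stake. The first is patient safety: Section 5.6.1 describes Grade 4 as life threatening, with pressor or ventilatory support indicated, and a site relying on 5.1.3 could redose such a patient. The second is compliance: a site that redoses follows 5.1.3 and breaches 7.5, so neither the site nor the coordinating center can say whether a deviation under Section 15 has occurred.

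Only later re-challenge is in conflict. Nothing in 5.1.3 contradicts the acute care described in 5.6.1.

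**Working it through.** The plan has no figure to reproduce here, so the check is a comparison of texts followed by a count of exposure.

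**Step 1. The rules side by side**

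| Section | Grade 3 infusion reaction | Grade 4 infusion reaction |
|---|---|---|
| 5.1.3 | More nivolumab possible, investigator decides | Same |
| 5.6.1 | Permanent stop | Permanent stop |
| 7.5 | Stop, whatever the duration | Stop, because it is not a listed exception |

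**Step 2. Can they be reconciled?**

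- The local-modification clause belongs to 5.6.1 and could soften that section alone. It does not reach 7.5, which contradicts 5.1.3 without help.
- Section 7.5 says so where it wants discretion: for some Grade 4 endocrine events and for interruptions longer than 6 weeks. It gives none for infusion reactions.
- The 7.5 lead-in is worded as a recommendation, but its Grade 3 infusion-reaction line is worded as a requirement.
- Sections 5.1.1 and 5.1.3 do cite 5.6.1, but only for infusion interruptions and for premedication after Grade 1 or 2 reactions. Neither points to the stop rule.
- No clause says which section prevails.

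**Step 3. Would another provision catch it?**

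- Section 7.3 generally lets treatment resume once a drug-related event is back to Grade 1 or baseline. An acute reaction can reach that before the next dose, which under 5.1.1 is at least 12 days away.
- Unacceptable toxicity in Section 5.2 needs a Grade 3/4 event that has not resolved to Grade 1/2 within 14 days, or a regimen-related death. A reaction that resolves sooner does not count toward the stopping rule in Section 12.3.
- Under 5.6.1, Grade 3/4 reactions are SAEs if criteria are met. Under 14.2.2, non-COH sites report qualifying SAEs within 24 hours. This notifies the study PI but does not require approval before redosing.

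**Step 4. Exposure**

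Inputs: 22 expected new Cohort B patients (Section 12.1.1), and 3 planned nivolumab doses plus an optional fourth (Section 5.1.5).

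- Infusions: 22 × 3 = 66 to 22 × 4 = 88.
- Infusions followed by another planned dose: 22 × (3 − 1) = 44 to 22 × (4 − 1) = 66.

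Only a reaction at one of those 44 to 66 infusions can lead to re-challenge within the planned schedule.

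**Step 5. How often might it happen?**

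The documents give no Grade 3/4 rate. What they do give is indirect:

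- Section 2.2.4: infusion reaction is among the most common drug-related events of any grade in the Hodgkin phase II trial, but is not among the Grade 3 or 4 events named. It is not named among the Grade 3 events of the 23-patient phase I trial, which had no Grade 4 or 5 events. The Grade 3 lists may not be complete.
- Section 2.2.6: infusion-site and hypersensitivity reactions of 1.7%, 3.7% and 18.5% at 0.3, 2 and 10 mg/kg, all Grade 1-2. The trial dose is 240/80 = 3 mg/kg at 80 kg, and below 240/40 = 6 mg/kg for every eligible patient (over 40 kg).
- Section 6.1 (N = 14,192, ungraded): infusion-related reaction from 1/1,000 to below 1/100, and anaphylactic reaction from 1/10,000 to below 1/1,000. Applied to 22 patients, this gives 22 × 0.001 = 0.022 to 22 × 0.01 = 0.22 patients, and 22 × 0.0001 = 0.0022 to 22 × 0.001 = 0.022 patients.

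The Section 6.1 band sits oddly with the phase II statement that the reaction was among the most common events, so these ranges are illustrations and not estimates. All three sources suggest that a severe reaction is rare.

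**The case against.** The strongest reply accepts the mismatch and disputes its weight. Section 5.1.3 is about premedication and is only permissive. The two sections that govern reaction management and stopping both say stop. A site handling an acute reaction must turn to 5.6.1 for the steps, and the stop sentence is in the same paragraph. Treating the dedicated stopping criteria as controlling is a reasonable reading. The event is rare, and nothing statistical depends on it.

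Much of this stands. The practical risk is small, and most investigators would stop. Three narrower points also stand:

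- The correction is a protocol amendment, and Section 17.3 requires IRB approval before changes take effect, so it costs more than a memo.
- The figure of 22 patients belongs to text dated April 2021. The documents do not say how many of them remained to be treated under Version 14, so the infusion counts are maxima for that group.
- The dose comparison is weak evidence, because earlier experience used 60-minute infusions and this trial uses about 30 minutes.

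None of this removes the contradiction. A reasonable reading is not a written precedence rule, and the document's own pointer for infusion reactions leads to the permissive section. Rarity limits the expected harm, but it is not a reason to keep two opposite rules for a potentially fatal event.

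**Conclusion.** The concern holds. For a Grade 3 or 4 infusion reaction, 5.1.3 cannot be squared with 5.6.1 and 7.5, and 5.1.1 directs sites to the wrong one of the three. The conclusion rests on the text alone and needs no assumed rate.

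Its size is modest. On the assumption that all 22 expected new Cohort B patients were still to be treated, at most 66 infusions would have a later planned dose, and severe reactions are expected to be rare. No endpoint, sample size, error rate or analysis changes. It should be fixed because the safety rule is wrong as written and the correction is small.

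**What to change.** 1. Replace the last sentence of 5.1.3 with a rule that matches the other sections, for example: *After any Grade 3 or 4 infusion-related reaction, nivolumab is stopped permanently (see Sections 5.6.1 and 7.5).*
2. In 5.1.1, change the reference for managing acute infusion reactions from 5.1.3 to 5.6.1.
3. Send the sites a memo drawing attention to the rule.

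If the sponsor does intend re-challenge, the amendment must go the other way: change 5.6.1, and change both the Grade 3 line and the Grade 4 exception list in 7.5.

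The cost is one sentence, one cross-reference and a memo, plus IRB review at the lead site and then at the participating sites. That review adds little if the edit is bundled with another amendment. No procedures, patients or analyses are added.
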